6.3.1.2 Analysis of secondary endpoints

Based on a 2x2 table included the primary endpoint (event/ event free) vs. risk stratification ("high"/- "low"-risk) we will calculate sensitivity, specificity and numbers need to screen for CKD273 and tested for significance using Chi-square test. In a logistic model we will added value using AUC and ROC with comparison between "high"- and "low"-risk vs. event and event-free for both primary endpoint. The logistic models will be performed both unadjusted and adjusted for age, gender, HbA_{1c}, systolic blood pressure, retinopathy, eGFR and UACR at baseline.

For the Cox-regression model a model, including adjustment for age, gender, Hba1c, systolic blood pressure, retinopathy eGFR and UACR at baseline will be comprised for secondary endpoints (see section 6.1.1 and 6.1.2, excluding 6.1.2 C, H and J).

For further clarification of the added value for discrimination, the rIDI will be calculated based on all above described Cox-regressions models with a significant HR for CKD273 in the unadjusted model for each endpoint.

To evaluate changes in UACR and eGFR over time (outcome measurement C and H in section 6.2.1) a linear mix model will be applied with adjustment for eGFR and UACR at baseline.

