## 15 STATISTICAL CONSIDERATIONS

### 15.1 Sample size considerations

The expected relative proportions of diabetes type 2 patients developing microalbuminuria within the planned study period are: 24% in patients at high-risk for diabetic nephropathy in the treatment group receiving active study medication, 40% in those patients at high-risk for diabetic nephropathy in the placebo treated group and 8.5% in those therapy-naive patients at low-risk for diabetic nephropathy. Using the samples size formula for two proportions test ( $\alpha=0.05$   $\beta=0.80$ ), randomized (1:1),  $n=129$  in each arm of the intervention group. To account for an expected drop-out frequency of approx. 10% we plan to randomize 300 high-risk patients to double blind treatment with spironolactone treatment or matched placebo.

High-risk patients are expected to comprise 15% of the screened and included patients. In order to identify 300 high-risk patients the study requires 2000 patients to be included. To take screen failures of approx. 25% into account, we expect to screen 2700 patients.

Recruitment will continue until a minimum of 300 high risk patients are enrolled in order to preserve statistical power. Furthermore, at least 2000 patients in the overall study cohort will be included.

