4.3.2 Observational cohort

All participants with valid proteomic score and data at baseline visit.

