6.3.1.3 Sensitivity analysis

In order to out-balance the fact that the "high"-risk stratum has primary outcome measures every third month we will perform a sensitivity analysis on the primary endpoint. Any primary endpoint in the "high"-risk stratum between annual visits will be carried forward to the date of the following annual visit. This analysis is most likely underpowered because of exclusion of endpoints in the high-risk stratum, however, the trend of the primary analysis is expected.

As in the "high"-risk group we have participants allocated to either active IMP or placebo we potentially limit the number of endpoints if the active IMP is beneficial. To adjust for this potential effect, we will perform a sensitivity analysis on the primary endpoint only in "low"-risk participants and in "high"-risk participants allocated to placebo treatment. This analysis is most likely also underpowered because of exclusion of endpoints in the "high"-risk stratum, however the trend of the primary analysis is expected.

ANOVA models for each continuous variable measured at baseline: age, HbA_{1c}, systolic blood pressure, Study site, eGFR and UACR will be tested within each stratum "high"- and "low"-risk as well as interaction in the Cox-model between strata with the primary endpoint as determinant. Chi square tests will be used for categorical variables: gender, use of antihypertensive agents, known cardiovascular disease and retinopathy.

We expect a correlation between the “high”-risk stratum and events of the primary endpoint for participants with known risk factors for overt kidney disease (higher age, HbA_{1c}, systolic blood pressure, UACR, and lower eGFR, male gender, use of antihypertensive agents, known cardiovascular disease and retinopathy).

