6.4 Additional analysis

For the per protocol cohort Cox-regression models will be performed both unadjusted and adjusted using treatment allocation as determinant and testing the primary outcome. Adjustment will include: Age, gender, HbA_{1c}, systolic blood pressure, retinopathy, eGFR and UACR at baseline. To examine added value for discrimination rIDI will be calculated for on all above described Cox-regression models.

In the observational cohort excluding all participants allocated to active treatment Cox-regression models will be performed to evaluate the hazard ratio between the “high”-risk without potential influence of the active treatment and the “low”-risk stratum. The model will be performed both on all available data and on censored data only (including annual samples). The models will be achieved unadjusted and adjusted for Age, gender, HbA_{1c}, systolic blood pressure and presence of retinopathy, eGFR and UACR at baseline. To examine added value for discrimination the rIDI will be calculated for all above described Cox-regression models.

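### SAP 6.3.1.2 measures the accuracy of CKD273 with spironolactone and placebo patients pooled as high-risk, and no placebo-only version of the 2x2 or AUC measures is named

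*SAP*

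**What the plan says.** SAP 6.3.1 is run in the observational cohort, which SAP 4.3.2 defines as "All participants with valid proteomic score and data at baseline visit". That takes in the low-risk stratum and both randomised arms.

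In this cohort SAP 6.3.1.2 crosses event status with high or low risk: "we will calculate sensitivity, specificity and numbers need to screen for CKD273 and tested for significance using Chi-square test". It then adds logistic models with AUC and ROC, unadjusted and adjusted. It gives no split, exclusion or weight for treatment allocation.

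Two later sections take up the treatment issue.

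- SAP 6.3.1.3 acknowledges that, with "participants allocated to either active IMP or placebo we potentially limit the number of endpoints if the active IMP is beneficial". It plans a sensitivity analysis on the primary endpoint in low-risk plus placebo high-risk patients. It names no statistic and refers to the expected trend of the primary analysis, which in 6.3.1.1 is a Cox model.
- SAP 6.4 adds: "In the observational cohort excluding all participants allocated to active treatment Cox-regression models will be performed". It attaches rIDI to those models.

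Protocol 15.6 plans predictive values, sensitivity, specificity and a c-statistic for the primary endpoint, and names no placebo-only set for them.

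**The concern.** The primary objective is to confirm that the urinary test predicts microalbuminuria. A reader will judge the test largely on sensitivity, specificity, number needed to screen and AUC. In the pooled table, a high-risk patient who stays event-free because of spironolactone is scored as an error of the test. The better the drug works, the worse the test looks.

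The trial is designed to show that the drug works (SAP 2.4, Hypothesis 2). The hazard ratio has named placebo-only versions; these accuracy measures do not.

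A smaller, separate point concerns outcome K, hyperkalaemia. It stays in the high-versus-low Cox list of 6.3.1.2, because only C, H and J are excluded. About half of the high-risk stratum is allocated to a drug for which Protocol 11.3 lists hyperkalemia as a side effect, and that stratum is also tested more often. The resulting hazard ratio would mix marker, drug and measurement frequency.

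**Working it through.** **The plan's own figure.** Protocol 15.1 and SAP 3.4 give 129 per arm for 40% against 24%, alpha 0.05 and power 0.80. With unpooled variance and two-sided alpha:

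n = (1.960 + 0.842)² × (0.40×0.60 + 0.24×0.76) / 0.16² = 129.5.

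The stated 129 is reproduced to within rounding. The documents give no expected accuracy figure for this trial, so the rest is an expected 2x2 table at the same planning rates.

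**Inputs.** 2000 patients, 15% high-risk, so 300 high-risk and 1700 low-risk (Protocol 15.1, 6.2). Event risks are 24% active, 40% placebo and 8.5% low-risk. Allocation is 1:1. Assumption: complete follow-up.

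**Formulas.** Sensitivity = TP/(TP+FN). Specificity = TN/(TN+FP). For a binary test, unadjusted AUC = (sensitivity + specificity)/2. In every version FN = 1700×0.085 = 144.5 and TN = 1700 − 144.5 = 1555.5.

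- **Pooled, as in 6.3.1.2.** High-risk event risk = (0.24+0.40)/2 = 0.32, so TP = 96 and FP = 204. Sensitivity 96/240.5 = 39.9%; specificity 1555.5/1759.5 = 88.4%; AUC 0.642.
- **Placebo patients weighted by 2.** TP = 2×60 = 120 and FP = 2×90 = 180. Sensitivity 120/264.5 = 45.4%; specificity 1555.5/1735.5 = 89.6%; AUC 0.675.
- **Active arm deleted, no weight.** TP = 60 and FP = 90. Sensitivity 60/204.5 = 29.3%; specificity 1555.5/1645.5 = 94.5%; AUC 0.619. The high-risk share falls from 15% to 150/1850 = 8.1%, and this distortion would occur even if the drug did nothing.

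**Number needed to screen.** The SAP does not define it. Read as patients screened per event flagged, it is 2000/96 = 20.8 pooled and 2000/120 = 16.7 weighted. Read as 1/risk difference, it is 1/(0.32−0.085) = 4.3 and 1/(0.40−0.085) = 3.2.

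**Dependence on the drug effect.** With half the planned effect (active 32%), pooled TP = 108 and FP = 192, giving sensitivity 42.8%, specificity 89.0% and AUC 0.659. With no effect (active 40%), the pooled figures equal the weighted ones.

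**Precision.** Simulated 95% ranges from binomial draws at 1700/150/150: sensitivity 39.0–51.5% weighted and 34.6–45.4% pooled; AUC 0.638–0.711 weighted and 0.612–0.672 pooled.

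**Hyperkalaemia.** From Protocol Table 1, high-risk potassium checks after baseline to week 104 are week 2 plus eight 13-weekly visits, which makes 9. Low-risk checks are weeks 52 and 104, which makes 2.

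**The case against.** **The placebo-only analysis may already cover these measures.** SAP 6.3.1.3 says only that it concerns the primary endpoint, and the 2x2 table and logistic models also use that endpoint. This stands in part: limiting 6.3.1.3 to Cox is an inference from its reference to the primary analysis. But if the section does cover the 2x2 table, running it as described means deleting the active arm, and that moves sensitivity to 29.3%, further from 45.4% than the pooled 39.9%. Written instructions are needed on either reading.

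**The counts can be recovered.** SAP 6.3.2.2 plans a 2x2 table of primary endpoint by treatment, so the weighted unadjusted figures could largely be worked out by hand, apart from any difference between the cohorts in 4.3.2 and 4.3.3. Protocol 15.6 also plots all three groups. This stands, and it lowers the stakes. The adjusted AUC in placebo patients cannot be recovered in this way.

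**The net direction is unknown.** By week 104 the high-risk stratum has 8 scheduled UACR visits and the low-risk stratum 2, before the end-of-study visit. More testing can raise the high-risk event count and so act against the pooling effect. The planning rates refer to "developing microalbuminuria within the planned study period", with no statement of the sampling schedule behind them, so this effect cannot be sized. This stands.

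Four stronger readings are tempting, and the documents do not support them.

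- That the SAP departs from the protocol on accuracy. The placebo-first order in Protocol 15.7 governs the secondary endpoints of section 5.5; the accuracy measures sit in 15.6, which sets no such order.
- That the carry-forward in 6.3.1.3 leaves the 2x2 table untouched. Endpoints "between annual visits will be carried forward to the date of the following annual visit" suggests that only dates move, but the same paragraph says "This analysis is most likely underpowered because of exclusion of endpoints in the high-risk stratum". The text is ambiguous.
- That the placebo-only rIDI in 6.4 is wrong without weights. The documents give nothing from which to size an error in a relative measure built on Cox models.
- That the unequal sampling is left unaddressed. For the placebo-only Cox models, 6.4 says: "The model will be performed both on all available data and on censored data only (including annual samples".

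**Conclusion.** The point holds for the 2x2 measures and the logistic AUC in SAP 6.3.1.2. As written, they describe the test in a cohort where about half of the high-risk patients are allocated to active drug, and no placebo-only version of them is named. At the planning rates, pooling lowers expected sensitivity by 5.5 points, specificity by 1.2 points and unadjusted AUC by 0.033. These sizes assume complete follow-up, a 15% high-risk share and the planned drug effect. They describe the pooling component alone and shrink to zero if the drug has no effect. The effect on the adjusted AUC cannot be derived from the documents.

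A reader might infer that the published accuracy will certainly understate the test. That goes too far, because unequal UACR sampling may offset some or all of the difference. Nor does the point undermine the primary hazard ratio, which has planned placebo-only versions. It is a worthwhile and inexpensive improvement to the secondary accuracy measures.

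**What to change.** Add to SAP 6.3.1.2:

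- The 2x2 measures and the unadjusted and adjusted logistic/AUC models will also be reported in low-risk plus placebo-allocated high-risk patients. Each placebo patient is weighted by 2, the inverse of the 1:1 allocation probability, with robust or bootstrap intervals. These results stand beside the pooled figures and do not replace them.
- Observed risk of the primary endpoint will be shown for the low-risk, high-risk placebo and high-risk active groups.

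For outcome K, report active against placebo under 6.3.2.2, and state that the pooled high-versus-low hazard ratio is not to be read as an effect of the marker.

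The cost is SAP wording and one weight variable, with no new data. The price is precision: about 150 rather than 300 high-risk patients inform the weighted figures. The simulated range for sensitivity widens from 10.8 points (34.6–45.4%) to 12.5 points (39.0–51.5%). The two ranges overlap, which is a further reason to show both versions.

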### CKD Biomarker panel

Proteomics is the analysis of large number of proteins or polypeptides in tissue and body fluids. Capillary electrophoresis-mass spectrometry (CE-MS) enables reproducible and robust high-

resolution analysis of several thousand low-molecular-weight urinary proteins/peptides in about one hour (17). Urine holds several advantages over blood in clinical proteomics. It can be collected non-invasively and its proteome is relatively stable (18). Members of the consortium have successfully identified a urinary biomarker pattern including 273 peptides significantly associated with chronic kidney disease (CKD273) (19).

Importantly, the biomarker panel has been validated in a multicentric approach involving >1000 blinded samples (20;21). The accuracy was high (96% sensitivity and 98% specificity), when evaluating only the diabetic patients in the test-set. To test the CKD273 pattern as a tool for early detection of DN, we recently performed an independent longitudinal study of normoalbuminuric diabetic patients at inclusion (22). The urinary CKD273 pattern distinguished progressing patients from non-progressing patients. The corresponding receiver operating characteristic (ROC) analysis resulted in an area under the curve (AUC) of 0.925 assuming a prevalence of 30% for DN. The positive predictive value was 97% and the negative predictive value was 88%. The specificity of the CKD273 pattern was further evaluated in patients without any evidence for renal impairment based on clinical history, creatinine, or urinary protein levels resulting in an overall specificity of 98%.

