#### 15.1.1 Considerations of risk stratification

The study population will be stratified based on the CKD273 score at the screening visit. Patients with a CKD273 biomarker score above the level of 0.154 are classified as high-risk patients. The level of the cut-off is based on previous publications and unpublished data from >800 subjects with type 2 diabetes (20;22).

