## 15.6 Analysis of primary endpoint

The primary endpoint is defined as time to the first occurrence of microalbuminuria (UACR >30 mg/g and <300 mg/g) in 2 out of 3 sterile first morning void urine samples with a geometric mean of UACR >30% above initial geometric mean UACR OR geometric mean > 40 mg/g in three samples. The baseline urinary albumin-to-creatinine ratios are the geometric mean of three measurements obtained during the "run-in" period.

It is expected, that the number of patients who will drop out between randomization and occurrence of microalbuminuria will be low (<15%).

If those cases where drop out occurs before sampling during the study period, prior to unblinding the treatment code it will be specified in the statistical analysis plan, whether these patients have to be considered as a treatment failure in the analysis of the primary endpoint.

The predictive value of a positive and negative test, specificity and sensitivity of the test in relation to prediction of development of the primary endpoint will be evaluated. To assess whether CKD273 classifier (the marker) improved risk prediction of the primary outcome we determined the concordance statistic (c-statistic) and Integrated Discrimination Improvement (IDI). Both parameters measure the discriminative ability of a marker in a model to distinguish between people who will or will not develop the outcome (in case of predictive methods).

The primary endpoint will be analyzed in the total population with comparisons of high- vs. low-risk pattern and active vs. placebo treatment using a Cox proportional-hazards regression model with treatment as a fixed effect; the baseline urinary albumin-to-creatinine ratio will be logarithmically transformed (base 10) as a covariate, and a two-tailed Wald chi-square test with an alpha level of less than 0.05; hazard ratios and two-sided 95 % confidence intervals will be calculated. Kaplan Meier plots of the groups will be made.

Secondly, the analyses will be adjusted for age, gender, center, HbA1c and BP. Thirdly, further adjustment for any baseline demographic variables which are significantly different between the groups and related to albuminuria at baseline will be calculated. In addition adjustment will be made for significant changes in RAAS blockade or treatment with aldosterone receptor antagonist as concomitant medication during the study period.

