5.5 Base characteristics / data description

Variable (reporting methods, [unit])

- Gender (N, % male)
- Medical history
 - o Diabetes duration (mean, SD, [years])
 - o Cardiovascular disease, hypertension, dyslipidemia [%]
 - o Retinopathy/ maculopathy (grade, [%])
 - o Smoking (grade, [%])
- Concomitant medication
 - o Use of antidiabetic medication (active substance group, [%])
 - o Use of antihypertensive agents (active substance group, [%]).
- Vital signs
 - o Systolic and diastolic blood pressure (Mean, SD, [mmHg]).
- Blood sample
 - o Creatinine, sodium, and potassium, HbA_{1c}, cholesterol, HDL, LDL, and triglycerides. (mean, SD)
- Urine sample
 - o Proteomic score (CKD273) (high, low-risk) (N, mean, [%])
 - o Urine albumin to creatinine level. (median, IQR, [mg/g])

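### Sensitivity and specificity of CKD273 come from a 2x2 table with no time horizon, so they depend on the mix of follow-up, and the unadjusted logistic AUC adds nothing to that table

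*SAP*

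**What the plan says.** The primary objective (Protocol 5.1, SAP 2.3.1) is to confirm that urinary proteomics predicts microalbuminuria. The primary test is a Cox comparison of the high- and low-risk strata (SAP 6.3.1.1).

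Test accuracy is handled in SAP 6.3.1.2, in three steps:

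- A 2x2 table of event or event-free against high or low risk gives sensitivity, specificity and the number needed to screen.
- A logistic model follows: "In a logistic model we will added value using AUC and ROC with comparison between" the two risk groups and the two outcome states. The SAP adds: "The logistic models will be performed both unadjusted and adjusted for age, gender", HbA1c, systolic blood pressure, retinopathy, eGFR and UACR.
- A further measure is taken from the Cox models: "For further clarification of the added value for discrimination, the rIDI will be calculated based on all above described Cox-regressions models" that show a significant unadjusted hazard ratio for CKD273.

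No horizon is given for any of these. SAP 5.3.2 plans at least two and at most 4.4 years of observation. SAP 5.4 keeps withdrawn patients in the analysis up to their last observation. SAP 6.2 applies no method for missing data and says that nothing will be censored.

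Both event times and a numeric score are available. Protocol 15.6 says "The primary endpoint is defined as time to the first occurrence of microalbuminuria". Protocol 15.1.1 says "Patients with a CKD273 biomarker score above the level of 0.154 are classified as high-risk patients", and SAP 5.5 describes the score at baseline: "Proteomic score (CKD273) (high, low-risk) (N, mean". No model in the SAP is specified with the score as a continuous predictor.

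**The concern.** Sensitivity and specificity for an event that accrues over time have meaning only at a stated time. Here, one table mixes patients seen for 2 years with patients seen for up to 4.4 years. A patient who leaves early without a recorded event falls in the event-free cell, because neither SAP 5.4 nor SAP 6.2 offers another place. The figures then describe this trial's recruitment calendar and withdrawal pattern as well as the test, and cannot be carried to another setting.

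The AUC does not repair this. With a two-level predictor, the unadjusted ROC curve has one interior point, and its area restates the table. The adjusted models have a full curve, but their AUC also reflects UACR, eGFR and the other covariates. Unless the same model is fitted without CKD273, the AUC does not show what the test adds.

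**Working it through.** **Inputs.** High-risk share 15% (Protocol 15.1). Event risks 40% (high-risk placebo), 24% (high-risk active) and 8.5% (low-risk) (SAP 3.4). A 1:1 mix of the high-risk arms gives (40% + 24%)/2 = 32%.

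**The plan's own figure.** The documents state no planned sensitivity, specificity or AUC for this trial. The one design figure built on these rates, 129 per arm, reproduces with the unpooled two-proportion formula (two-sided 0.05, power 0.80): (1.960 + 0.842)² × (0.40×0.60 + 0.24×0.76)/0.16² = 129.5. The present point does not affect it.

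**Accuracy at the planned rates.** With share π and risks H (high) and L (low):

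- sensitivity = πH / [πH + (1−π)L]
- specificity = (1−π)(1−L) / [1 − πH − (1−π)L]
- AUC of a two-level marker = (sensitivity + specificity)/2

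| High-risk event rate | Sensitivity | Specificity | AUC |
|---|---|---|---|
| 40% | 0.0600/0.13225 = 0.454 | 0.77775/0.86775 = 0.896 | 0.675 |
| 32% | 0.0480/0.12025 = 0.399 | 0.77775/0.87975 = 0.884 | 0.642 |

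**Effect of follow-up.** The documents do not say at what time the planned risks apply, so both ends were tried, with constant hazards (assumption) and the 32% mix. If the risks apply at 2 years, those at 4.4 years are 1 − 0.68^2.2 = 0.572 and 1 − 0.915^2.2 = 0.178.

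| Planned risks apply at | Follow-up | Sensitivity | Specificity | AUC |
|---|---|---|---|---|
| 2 years | 2 years | 0.399 | 0.884 | 0.642 |
| 2 years | 4.4 years | 0.362 | 0.916 | 0.639 |
| 4.4 years | 2 years | 0.418 | 0.866 | 0.642 |
| 4.4 years | 4.4 years | 0.399 | 0.884 | 0.642 |

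The test is the same in every row. Sensitivity moves by 0.02 to 0.04 and specificity by 0.02 to 0.03; the AUC is almost fixed.

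**Effect of early leavers (illustration).** SAP 3.4 expects 10% drop-out in the intervention part. Take the extreme case that all of them leave before any event could be recorded.

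- In both strata alike (H = 0.9 × 0.32 = 0.288, L = 0.9 × 0.085 = 0.0765): sensitivity stays at 0.399 and specificity goes from 0.884 to 0.880. The positive predictive value falls from 0.320 to 0.288, and the negative rises from 0.915 to 0.924.
- In the high-risk stratum only: sensitivity = 0.0432/0.11545 = 0.374 and specificity = 0.77775/0.88455 = 0.879.

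**Number of ROC points.** In a simulated cohort of 1811, the unadjusted logistic model had 2 distinct predictions. Adding one continuous covariate gave 1811. The one-point curve is therefore confined to the unadjusted model.

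**Continuous score (illustration).** The documents give no score distribution. With a normal score cut at its 85th percentile and a logistic risk calibrated to the planned rates, the score has an AUC of about 0.75 where the binary result has 0.642, and about 0.79 where it has 0.675.

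**The case against.** The high/low result is the test that the trial sets out to confirm. Both SAP hypotheses concern the two strata, and 0.154 is prespecified and decides who is randomized. Sensitivity and specificity at that cut-off are the right operating measures, and judging whether 0.154 is a good cut-off is not an objective. The primary comparison uses event times, and so does the rIDI, which SAP 6.4 repeats without active-arm patients. Protocol 14.6 asks sites to keep pursuing endpoints after study drug stops. Protocol 15.7 plans to explore whether the CKD273 pattern predicts endpoints within the high-risk group. All of this stands, and it confines the point to secondary reporting of accuracy.

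Four stronger conclusions that a reader might draw are not supported:

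- **That the discrimination analysis as a whole is a one-point ROC.** The adjusted logistic models and the rIDI are not.
- **That the protocol's c-statistic was dropped.** Protocol 15.6 says "we determined the concordance statistic (c-statistic) and Integrated Discrimination Improvement (IDI" without naming a survival version, and a logistic AUC is itself a c-statistic.
- **That an AUC of 0.64 to 0.67 contradicts the background figure, where a ROC analysis "resulted in an area under the curve (AUC) of 0.925".** That figure comes from another cohort, at an assumed prevalence of 30%. The planning values here are unadjusted and binary.
- **That the trial cannot show discrimination.** The score and event times are held, and Protocol 15.5 allows further analyses as exploratory.

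The objection leaves three things unanswered. The 2x2 table still has no horizon. The rIDI has none either, is conditional on a significant hazard ratio, and is specified on the high/low factor. No reference model is named for the AUC.

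**Conclusion.** The point holds as a limited one. The planned sensitivity and specificity have no horizon and count early leavers as event-free. From follow-up length alone, they shift by about 0.02 to 0.04 at the planned rates. This rests on constant hazards, a 15% high-risk share, a 1:1 mix of arms, and an assumed time for the planned risks. Withdrawal adds little if it is equal in the strata; in the extreme case above, confined to the high-risk stratum, it lowers sensitivity by 0.025. The AUC is robust to follow-up, but its unadjusted form carries no information beyond the table. Neither hypothesis test nor the sample size is affected. Because prediction is the primary objective, interpretable accuracy figures are worth fixing in advance.

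**What to change.** Keep the 0.154 classification and the primary Cox analysis. In SAP 6.3.1.2:

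1. Estimate sensitivity, specificity, and positive and negative predictive values from Kaplan-Meier risks in each stratum, put into the formulas above, at one fixed horizon. Set it just after the week-104 visit window closes (104 weeks + 14 days = 106 weeks). Censor at the last UACR assessment and reconcile SAP 6.2 with this. Protocol 15.6 already lists the predictive values.
2. Report a time-dependent AUC, or Harrell's or Uno's C, at that horizon for models with and without CKD273 on top of the baseline covariates, including UACR.
3. Add the continuous CKD273 score as a supplementary predictor.

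Two design features must be handled, or the new figures will mislead.

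- **Sampling.** The high-risk group is sampled every 13 weeks and the low-risk group yearly. Run these analyses with high-risk events moved to the next annual visit, as SAP 6.3.1.3 already plans. That aligns dates but not the number of chances to detect an event; the annual-samples version in SAP 6.4 serves as a check.
- **Treatment.** About half of the high-risk stratum takes spironolactone. Repeat the analyses in the SAP 6.4 cohort without active-arm patients, and restore the full-cohort high-risk share, for example by giving placebo patients a weight of 2. Without this, the share falls to 0.075/0.925 = 8.1%, and sensitivity at the planned rates would read 0.030/0.10225 = 0.293 instead of 0.454.

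The cost is a few more outputs from data already held, and less precision where active-arm patients are left out.
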